12.6.4 Exploratory Efficacy Analyses

12.6.4.1 Severity Assessment of COVID-19 Cases

All COVID-19 cases meeting the primary efficacy case definition are classified as mild, moderate or severe. An additional category “moderate to severe” is created, combining moderate and severe cases. The number and percentage of subjects with mild, moderate, severe and moderate to severe cases is summarized descriptively.

These summaries and analyses are provided based on the EAS and are provided for the interim analyses and the primary efficacy delivery.

The analysis contains all applicable cases available in the respective data cut.

12.6.4.2 Hospitalizations, Oxygenations, Mechanical Ventilations and Deaths

A summary table presents the number and percentage of subjects with any of the following events:

- Need for supplemental oxygenation due to COVID-19,
- Need for mechanical ventilation due to COVID-19,
- Hospitalization due to COVID-19,
- Death due to COVID-19,
- Death due to any cause.

This table is provided considering only virologically confirmed COVID-19 cases with an onset \geq 15 days after second vaccination. Thereby, the start date of the COVID-19 case leading to occurrence of any of the above must be \geq 15 days after second trial vaccination.

The summary for events with a start date \geq 15 days after second vaccination is based on the EAS.

The summary based on the EAS is provided for the second interim analyses and the primary efficacy delivery and contains all applicable cases available in the respective data cut.

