4.2.3 Exploratory Endpoints

Exploratory Efficacy Endpoints

- Occurrence of first episodes of virologically-confirmed (RT-PCR positive) cases of COVID-19 caused by individual VOCs (see Section 9.2.1.6).
- Severity assessment of first episodes of virologically-confirmed (RT-PCR positive) cases of COVID-19 meeting the case definition for the primary efficacy analysis (COVID-19 severity definitions provided in Appendix 3 and Appendix 4).

The following endpoints will be analyzed as occurring \geq 15 days following the second trial vaccination (full VE) and at any time after the first trial vaccination.

In SARS-CoV-2 naïve subjects:

- Occurrence of supplemental oxygenation due to COVID-19.
- Occurrence of mechanical ventilation due to COVID-19.
- Occurrence of hospitalization due to COVID-19.
- Occurrence of death due to COVID-19.
- Occurrence of death due to any cause.

In SARS-CoV-2 naïve and non-naïve subjects:

• In all subjects regardless of their baseline serostatus, occurrence of first episodes of virologically-confirmed (RT-PCR positive) cases of COVID-19 of any severity.

The following endpoint will be analyzed in subjects who had a first episode of a virologically-confirmed (RT-PCR positive) case of COVID-19 of any severity meeting the case definition for the primary efficacy analysis.

 Occurrence of second episodes of virologically-confirmed (RT-PCR positive) cases of COVID-19 of any severity.

Clinical Trial Protocol	CV-NCOV-004
CureVac AG	COVID-19 mRNA Vaccine

Exploratory Immunogenicity Endpoints

On Days 1, 29, 43, 120**, and 211** in peripheral blood mononuclear cells (PBMCs) from approximately 200*** subjects at selected site(s):

- The frequency and functionality of SARS-CoV-2 RBD of S-specific T-cell response after antigen stimulation by intracellular cytokine staining (ICS) to investigate Th1 response and expression of Th2 markers.
- The proportion of subjects with a detectable increase in SARS-CoV-2 RBD of S-specific T-cell response.

** Thereby, testing of samples collected on Day 120 and Day 211 will be done only in subjects categorized as T-cell responders on Day 29 and/or Day 43.

*** First testing of samples will be performed for a subset of these subjects and might be extended to 200 subjects if T-cell response is detectable.

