10.3.5.3 Exploratory Efficacy Endpoints Analyses

The proportions of COVID-19 cases of any severity caused by identified SARS-CoV-2 VOCs and mild, moderate, and severe COVID-19 cases (according to primary case definition) among all cases will be summarized by group.

Clinical Trial Protocol	CV-NCOV-004
CureVac AG	COVID-19 mRNA Vaccine

Description of frequencies and percentages will be provided by group for subjects who:

- Need supplemental oxygenation due to COVID-19.
- Need mechanical ventilation due to COVID-19.
- Are hospitalized due to COVID-19.
- Died due to COVID-19.
- Died due to any cause.

This will be done for events occurring \geq 15 days following the second trial vaccination (full VE) and then for events occurring at any time after the first trial vaccination.

The VE in the prevention of first episodes of virologically-confirmed cases of COVID-19 of any severity will be reassessed on all subjects whatever their serological status at baseline for cases occurring \geq 15 days following the second trial vaccination and then for all cases occurring after the first dose.

Finally, the number and percentage of subjects who developed a second episode of COVID-19 will be displayed by group.

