7.3.1 Exploratory Efficacy Objectives

To investigate in SARS-CoV-2 naïve subjects:

- If cases of COVID-19 are milder in severity in subjects receiving a 2-dose schedule of CVnCoV compared to those administered placebo.
- If the need for supplemental oxygenation due to COVID-19 is reduced in subjects receiving a 2-dose schedule of CVnCoV compared to those administered placebo.
- If the need for mechanical ventilation due to COVID-19 is reduced in subjects receiving a 2-dose schedule of CVnCoV compared to those administered placebo.
- If hospitalization due to COVID-19 is reduced in subjects receiving a 2-dose schedule of CVnCoV compared to those administered placebo.
- If mortality due to COVID-19 is reduced in subjects receiving a 2-dose schedule of CVnCoV compared to those administered placebo.
- If all-cause mortality is reduced in subjects receiving a 2-dose schedule of CVnCoV compared to those administered placebo.
- To investigate the cell-mediated immune (CMI) response of a 2-dose schedule of CVnCoV from approximately 200 subjects at selected site(s).

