9.3 Exploratory Endpoints

9.3.1 Exploratory Efficacy Endpoints

- Severity assessment of first episodes of virologically-confirmed (RT-PCR positive) cases of COVID-19 meeting the case definition for the primary efficacy analysis.
- The following endpoints are analyzed as occurring ≥ 15 days after the second trial vaccination (full VE).
 - In SARS-CoV-2 naïve subjects:
 - Occurrence of supplemental oxygenation due to COVID-19.
 - Occurrence of mechanical ventilation due to COVID-19.
 - Occurrence of hospitalization due to COVID-19.
 - Occurrence of death due to COVID-19.
 - Occurrence of death due to any cause.

Thereby, the start date of the COVID-19 case leading to occurrence of any of the above must be ≥ 15 days after second trial vaccination.

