
the serum of subjects who tested seronegative at baseline.
	
On Days 29, 43, (57,) 120 and 211 for subjects seropositive at baseline:
 
 • GM of FC from baseline with 95% CI of neutralizing antibodies to SARS-CoV-2 virus by group. 
On Days 29, 43, (57,) 120 and 211 for subjects seronegative at baseline:
 
 • Number and percentage with exact 95%CI of subjects by group for who a seroconversion is observed (detectable neutralizing antibodies to SARS-CoV-2 virus in the serum).
Exploratory Efficacy	

 • Severity assessment of first episodes of virologically-confirmed (RT-PCR positive) cases of COVID-19 meeting the case definition for the primary efficacy analysis 	
In naïve evaluable subjects (complying with the definition of Efficacy Analysis Set) who had a first episode of a virologically-confirmed (RT-PCR positive) case of COVID-19 of any severity meeting the case definition for the primary efficacy analysis:
 
 • The proportions of mild, moderate and severe COVID-19 cases among all cases by severity group

ENDPOINTS (subject level)	ESTIMANDS (population level)

The following endpoints are analyzed as occurring ≥ 15 days following the second trial vaccination (full VE).
 
 • Occurrence of supplemental oxygenation due to COVID-19. • Occurrence of mechanical ventilation due to COVID-19. • Occurrence of hospitalization due to COVID-19. • Occurrence of death due to COVID-19. • Occurrence of death due to any cause. 	
In naïve evaluable subjects (complying with the definition of Efficacy Analysis Set) at least 15 days following second vaccination:
 
Number and percentages by group of subjects who:
 
 • Need supplemental oxygenation due to COVID-19. • Need mechanical ventilation due to COVID-19. • Were hospitalized due to COVID-19. • Deceased due to COVID-19. • Deceased due to any cause.
Exploratory Immunogenicity	

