9.6.9 Summary of Analysis Sets to be Used per Analysis

Table 3Table 4 and Table 4Error! Reference source not found. below provide an overview on the Analysis Sets used for the analyses of each endpoint.

Table 3: Summary of Analysis Sets to be Used per Analysis - Efficacy Endpoints

ENDPOINT TYPE	ENDPOINT SHORT DESCRIPTION	ANALYSIS SET
PRIMARY EFFICACY ENDPOINT	First episodes of COVID-19 cases.	EAS
	First episodes of moderate to severe COVID-19 cases.	EAS
KEY SECONDARY EFFICACY ENDPOINT	First episodes of severe COVID-19 cases.	EAS
	“Wild type” and “Alpha” SARS-CoV-2 strains	EAS
	First episodes of COVID-19 cases in subjects ≥ 61 years of age	EAS*
OTHER SECONDARY EFFICACY ENDPOINT	First episodes of SARS-CoV-2 infection, with or without symptoms.	EAS
	BoD Scores	EAS
	First episodes of COVID-19 cases with symptom onset at any time after the first trial vaccination	SAS [#]
	Severity assessment of first episodes of COVID-19 cases	EAS
	Any strain COVID-19	EAS
	Supplemental oxygenation, mechanical ventilation, hospitalization, death (cases ≥ 15 days after second vaccination)	EAS
EXPLORATORY EFFICACY ENDPOINT	Supplemental oxygenation, mechanical ventilation, hospitalization, death (cases after first dose)	SAS
	First episodes of COVID-19 cases with symptom onset ≥ 15 days after second vaccination, regardless of baseline serostatus	SAS ^{\$}
	First episodes of COVID-19 cases with symptom onset at any time after the first vaccination, regardless of baseline serostatus	SAS

ENDPOINT TYPE	ENDPOINT SHORT DESCRIPTION	ANALYSIS SET
	Second episodes of COVID-19 cases	EAS

* RESTRICTED TO SUBJECTS ≥ 61 YEARS OF AGE

RESTRICTED TO SUBJECTS WITH NEGATIVE BASELINE SEROSTATUS

\$ RESTRICTED TO SUBJECTS WHO RECEIVED BOTH DOSES AS RANDOMIZED, DID NOT DEVELOP A COVID-19 CASE OR DISCONTINUED TRIAL PRIOR TO 15 DAYS AFTER SECOND VACCINATION

Table 4: Summary of Analysis Sets to be Used per Analysis - Safety and Immunogenicity Endpoints

ENDPOINT TYPE	ENDPOINT SHORT DESCRIPTION	ANALYSIS SET
	Occurrence, intensity and relationship of medically-attended AEs	SAS
	Occurrence, intensity and relationship of SAEs and AESIs	SAS
	Occurrence of fatal SAEs	SAS
PRIMARY SAFETY ENDPOINT^{\$}	Occurrence, intensity and duration of solicited local AEs	SASsol
	Occurrence, intensity and duration of solicited systemic AEs	SASsol
	Occurrence, intensity and relationship of unsolicited AEs	SAS 2
	Occurrence of AEs leading to vaccine withdrawal or trial discontinuation	SAS

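### SAP 12.6.4.2 limits the any-cause death row to confirmed COVID-19 cases, which the objective, the estimand and the protocol do not, and SAP 6.2 does not declare it

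*SAP*

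**What the plan says.** SAP 12.6.4.2 plans a count and percentage of subjects for supplemental oxygen, mechanical ventilation, hospitalisation and death, each due to COVID-19, and for death from any cause. The rule that follows applies to the table as a whole: "This table is provided considering only virologically confirmed COVID-19 cases with an onset" at least 15 days after dose 2. The next sentence requires that the case behind each listed event also start in that window. A further sentence assigns the EAS, and the section closes by saying that the summary "contains all applicable cases available in the respective data cut".

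Two other parts of the SAP bear on this. Table 3 in section 9.6.9 labels the same group in terms of cases: "Supplemental oxygenation, mechanical ventilation, hospitalization, death (cases" at least 15 days after the second vaccination). Section 9.3.1 places a sentence under its endpoint list saying that "the start date of the COVID-19 case leading to occurrence of any of the above must be" at least 15 days after dose 2.

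The rest of the plan has no such condition:

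- SAP 7.3.1, objective: "If all-cause mortality is reduced in subjects receiving a 2-dose schedule of CVnCoV compared to those administered placebo".
- SAP 9.5, Table 1, estimand: "Deceased due to any cause", in EAS subjects from 15 days after dose 2.
- Protocol 4.2.3, endpoint: "Occurrence of death due to any cause", with a time window only. The estimand in Protocol 4.3 agrees.
- Protocol 10.3.5.3, analysis: the window is set on the event itself ("This will be done for events occurring" at least 15 days after the second vaccination).

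SAP 6.2, which lists departures from Protocol version 4.0, mentions any-cause death only to drop the version counted from the first vaccination.

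**The concern.** All-cause mortality is worth reporting next to COVID-19 mortality because it needs no attribution of cause and would show a difference between arms in other deaths. A row that admits only confirmed cases can do neither. It becomes a count of deaths among people who had COVID-19, close to the row above it, under a label that promises something else. A reader could take it as the answer to the stated mortality objective. Because SAP 6.2 is silent, that reader has no notice that the definition changed.

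**Working it through.** The plan states no figure for this row, so there is none to reproduce. The check is a comparison of the texts, followed by one proportion to size the restriction.

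**Who can enter the row**

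| Source | Population | Time window | Confirmed case required? |
|---|---|---|---|
| SAP 7.3.1 objective | naïve subjects | none stated | No |
| SAP 9.5 Table 1 estimand | EAS | ≥ 15 days after dose 2 | No |
| Protocol 4.2.3, 4.3, 10.3.5.3 | naïve / EAS | event ≥ 15 days after dose 2 | No |
| SAP 9.3.1 endpoint | naïve subjects | ≥ 15 days after dose 2 | Unclear: case condition or timing rule |
| SAP 12.6.4.2 analysis | EAS | case onset ≥ 15 days after dose 2 | Yes |

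The later sentence in 12.6.4.2 about events with a start date names the analysis set. It does not lift the word *only* in the sentence before it.

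**Size**

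Inputs, from Protocol 3.1.4: 25,062 subjects in the final efficacy analysis and 228 adjudicated cases. The number of confirmed cases used for this table could differ slightly from 228.

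- Subjects able to enter the row: 228 / 25,062 = 0.91%, or about 1 in 110 (25,062 / 228 = 109.9).
- Subjects unable to enter it: 25,062 − 228 = 24,834, or 99.1%.

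Let *k* be the risk of non-COVID death in cases divided by that in non-cases. The largest share of non-COVID deaths that could reach the row is

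228*k* / (228*k* + 24,834).

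| *k* | Maximum share counted |
|---|---|
| 1 | 228 / 25,062 = 0.91% |
| 2 | 456 / 25,290 = 1.80% |
| 5 | 1,140 / 25,974 = 4.39% |

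The range of *k* is an assumption; the documents give no value. The shares are upper bounds, because a case can enter the row only after onset. If the sentence requiring the case to lead to the event is also taken literally, the share is close to zero for any *k*.

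The number of deaths affected, and any ratio between arms, cannot be calculated: the documents give neither deaths nor case fatality by arm.

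**The case against.** The strongest reply is that this is loose drafting and not a real restriction. A separate any-cause row makes little sense if only cases count. The sentence on case start dates can be read as a timing rule for events that have a case behind them, and the same sentence stands in SAP 9.3.1. The wording about applicable cases is stock text that also closes SAP 12.6.3.3 and 12.6.4.1. The list of outputs is kept outside the SAP (Appendix 4), so the documents do not show what was programmed.

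The second reply is that nothing is lost. Protocol 9.3.3 has all deaths reported as SAEs. SAP 12.7.1 and 12.7.1.3 tabulate fatal AEs by arm with no case condition, also in baseline seronegatives, and list them by subject. SAP 12.7.1.4 and 12.7.7 repeat them without censoring, the latter by vaccine received. EAS subjects received what they were randomised to (SAP 9.6.2), so as-treated tables do not move them between arms. With the listings of exclusions from each analysis set (SAP 12.1), a reader could probably pick out the EAS deaths.

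Much of this stands. The intent may have been correct, the row as delivered may be correct, and the number of deaths affected could be zero. It does not remove the conflict. The sentence containing *only* governs the whole table, and it is the rule a programmer would follow. If 9.3.1 is also a case condition, then two SAP sections, not one, disagree with the SAP's own objective and estimand. The fatal-AE tables run on the SAS from dose 1, so none of them gives EAS deaths from 15 days after dose 2. Rebuilding the count from listings is not the planned summary.

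**Conclusion.** The concern holds, and it is minor. As written, SAP 12.6.4.2 yields a count that is not the all-cause mortality estimand in SAP 9.5 and Protocol 4.3, and the departure is not declared. The restriction shuts out about 99% of the analysis population, taking the 25,062 subjects as the EAS and the 228 adjudicated cases as the table's cases. The percentage describes who could contribute; it does not estimate how many deaths were missed. The row is exploratory, descriptive and untested, few deaths are expected, and no efficacy conclusion depends on it. The finding concerns the written rule. Whether the delivered table followed it cannot be determined from the protocol and SAP.

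**What to change.** In SAP 12.6.4.2, apply the confirmed-case condition to the four rows due to COVID-19 only, and reword SAP 9.3.1 to match. For the any-cause row, count every EAS death dated at least 15 days after dose 2, up to the data cut-off, with the existing censoring for unblinding or receipt of an authorised vaccine (SAP 10.11). Do not stop follow-up at COVID-19 symptom onset. A count and percentage needs no entry in Table 11. Label any re-run post hoc, because SAP 6.1 states that version 5.0 was written and approved by an unblinded team.

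If the table is not to be re-run, first check the delivered output. If the row was restricted, relabel it as death from any cause among confirmed COVID-19 cases, add the restriction to SAP 6.2, and refer the reader to the fatal-AE tables. If it already counted all EAS deaths, keep the label and correct only the text.

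The cost is about one sentence in each of two SAP sections, plus one descriptive row if re-run. The relabelling route needs text edits in 12.6.4.2, 9.3.1 and 6.2. No new data are needed.

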12.6.5 Open-Label Analyses

In agreement with the Sponsor it was decided to not analyze the exploratory OL efficacy endpoint.

12.7 Safety Analyses

12.7.1 Adverse Events

Unsolicited AEs, including SAEs, and AESIs and solicited AEs integrated to or recorded on the CRF are coded using MedDRA Version 23.1 or higher, by SOC and PT.

Only TEAEs as defined in Section 10.5.1 are included in AE summaries. In AE listings, all AEs are included.

Solicited AEs occurring on the day of vaccination and the following 7 days are generally included in summaries if not otherwise stated.

Summaries of medically attended AEs only include those AEs that started up to 6 months after the second trial vaccination, see Section 10.5.6 for further details.

Note that for all summaries by SOC and PT, counting is by subject, not event and subjects are only counted once within each SOC and PT. However, if not stated otherwise, all summaries of unsolicited AEs include the number of AEs reported in each category and all events of a subject are then counted.

All AE summary tables are provided overall, by vaccine group, and by age group and vaccine group and are repeated separately in subjects seronegative at baseline and in subjects seropositive at baseline for SARS-CoV-2 N protein antibody levels (see Section 10.6.1).

In general, percentages are based on the number of subjects in the respective analysis set. In summary tables for AEs after the second vaccination, percentages are based on the number of subjects in the respective analysis set who have received the second vaccination.

12.7.1.1 Analysis of Unsolicited AEs

The following summaries of unsolicited AEs by SOC and PT are provided, separately for AEs occurring within the first 28 days after each vaccination, within the 28 days after any vaccination, and all reported AEs (including those reported later than 28 days after any vaccination):

- Occurrence of unsolicited AEs,
- Occurrence of related unsolicited AEs,
- Occurrence of unsolicited AEs by maximum severity (mild / moderate / severe),
- Occurrence of related unsolicited AEs by maximum severity (mild / moderate / severe)

Additionally, a summary of unsolicited AEs (excluding solicited AEs) occurring within the first 28 days after each vaccination and within 28 days after any dose that have a frequency of > 5% in at least one treatment arm (on PT level) by SOC and PT is provided. The summary is repeated for all reported AEs (including those reported later than 28 days after any vaccination).

Summaries of unsolicited AEs occurring within 28 days after each vaccination and within 28 days after any vaccination are provided based on the SAS 2. Summaries of all reported unsolicited AEs (including those reported later than 28 days after any vaccination) are provided based on the SAS.

Listings of unsolicited AEs and related unsolicited AEs are produced. These listings are excluding solicited AEs and flagging treatment emergent events.

